Injection Therapy in Patients with Lateral Epicondylitis

ID: 2018/12

Document Date: 05/13/2018

Study Protocol

The study was a single-blind randomized clinical trial with parallel group and allocation ratio was 1:1. Ethical approval of the study was obtained from the Inonu University Clinical Research Ethics Committee (No.2018/12). Volunteers meeting eligibility criteria gave informed written consent prior to enrolment by the trial administrator. The patients who met the inclusion criteria randomly assigned into two groups (PrT group, HA group) in a ratio of 1:1 through the stratified block randomization method. The patients and the researcher who were responsible for the analyzing of the data were blinded to the randomization results. All data were collected at baseline, 6 and 12 weeks. Furthermore, patients were monitored if they had any side effects from the injection such as ecchymosis, redness, increasing pain or reduced range of motion.

Statistical Analysis Plan

The SPSS (version23; SPSSInc., Chicago, IL, USA) was used to conduct the analysis. Descriptive statistics were presented as mean \pm standard deviation and percentage. In the evaluation of categorical variables, Pearson Chi-Square Test and Fisher's Final Test were used. Suitability of variables to normal distribution were analyzed using visual (histogram and probability graphics) and analytical methods (Shapiro-Wilk Test). Differences between the two groups at baseline and at six and twelve weeks were tested by Independent-samples t test. Paired t tests were used for within-group analyses. P values <0.05 were considered significant.

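### Allocation is by stratified blocks, but the week 6 and week 12 t tests ignore the strata; if the strata are prognostic the test is conservative and power is forgone.

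*Combined protocol and SAP*

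**What the plan says.** The Study Protocol section describes a "single-blind randomized clinical trial with parallel group and allocation ratio was 1:1" and assigns patients to the PrT or HA group "in a ratio of 1:1 through the stratified block randomization method". It does not name the stratification factors, the number of strata or the block size. On timing it says "All data were collected at baseline, 6 and 12 weeks".

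The Statistical Analysis Plan section gives the between-group analysis in one sentence: "Differences between the two groups at baseline and at six and twelve weeks were tested by Independent-samples t test". Of the within-group analysis it says "Paired t tests were used for within-group analyses". The criterion is "P values <0.05 were considered significant".

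No linear model, analysis of covariance or stratified test is mentioned. The document states no sample size, power, effect size or standard deviation.

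**The concern.** The design uses the strata and the analysis does not. Stratified blocking holds the arms in near-equal proportion within each stratum, so differences between strata contribute little to chance variation in the PrT minus HA difference. The two-sample t test estimates its error variance as if patients had been allocated without strata, and so it still counts those differences as noise.

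If the strata are unrelated to outcome, this makes practically no difference. If they are related, the reported standard error is too large, the P values are too large, and the 0.05 threshold is in effect stricter than stated. A false positive becomes less likely, not more. What is at stake is a real PrT versus HA difference that a stratum-adjusted analysis would detect and the t test would miss. Factors are usually chosen for stratification because they are expected to matter, so the condition is plausible, but the document does not show that it is met here.

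**Working it through.** **Inputs from the document.** 1:1 allocation by stratified blocks (Study Protocol); unadjusted t tests at weeks 6 and 12, significance at 0.05 (Statistical Analysis Plan). The document gives no power or sample size figure to reproduce.

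**Assumptions.** Two-sided test (not stated). R² is the share of outcome variance explained by the strata, taken as 0, 5, 10, 20 or 30%.

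**Closed form (normal approximation).** With arms balanced within strata, the true variance of the group difference is (1 − R²) times the variance that the t test estimates.

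- Overstatement of the standard error: k = 1/√(1 − R²)
- Actual type I error of the t test: 2 × [1 − Φ(1.960k)]
- If the t test has nominal 80% power (1.960 + 0.842 = 2.802): t test power = Φ(0.842k); adjusted power = Φ(2.802k − 1.960)

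At R² = 10%, k = 1/√0.9 = 1.054. Type I error = 2 × [1 − Φ(2.066)] = 3.9%. T test power = Φ(0.887) = 81.3%; adjusted power = Φ(0.993) = 84.0%.

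| R² | k | Type I error, t test | Power, t test | Power, adjusted | Points forgone |
|---|---|---|---|---|---|
| 0% | 1.00 | 5.0% | 80.0% | 80.0% | 0 |
| 5% | 1.03 | 4.4% | 80.6% | 82.0% | 1.4 |
| 10% | 1.05 | 3.9% | 81.3% | 84.0% | 2.7 |
| 20% | 1.12 | 2.8% | 82.7% | 87.9% | 5.3 |
| 30% | 1.20 | 1.9% | 84.3% | 91.8% | 7.5 |

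The last column is taken from unrounded powers.

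The loss depends on where power starts. If the t test's nominal power were 40%, the t test and adjusted powers would be 39.5% and 43.6% at R² = 10%, and 38.1% and 53.2% at 30%.

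A second, hypothetical reading supposes that the trial was sized so that the *adjusted* analysis has 80% power. The t test then has power Φ(2.802 − 1.960k): 80.0, 78.5, 76.9, 72.9 and 67.7% across the same R² values.

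**Simulation for a small trial.** The closed form ignores incomplete blocks and the degrees of freedom spent on strata. Settings, all assumed: 32 patients in total, 8 strata (three binary factors, additive effects), blocks of 4, 10,000 trials per row, effect size set for 80% t test power.

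| R² | t test | Main effects of factors | All stratum cells |
|---|---|---|---|
| 0% | 79.7% | 78.2% | 76.0% |
| 5% | 80.4% | 81.1% | 78.2% |
| 10% | 80.4% | 82.6% | 80.2% |
| 20% | 81.8% | 87.1% | 85.0% |
| 30% | 82.5% | 91.0% | 89.3% |

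Across settings with 2 or 8 strata and 32 or 60 patients, the t test's type I error was 5.1 to 5.3% at R² = 0, 4.1 to 4.3% at 10% and 1.9 to 2.5% at 30%. The main-effects model stayed at 4.8 to 5.3% throughout. A repeat of the 32-patient settings gave up to 2.7% for the t test at 30%.

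A separate simulation with 30 patients per arm and 4 strata (20,000 trials per setting) agreed. At R² = 10% the t test had type I error 3.9% and power 79.9%, against 4.9% and 82.7% adjusted. At 30% the figures were 2.1% and 82.6%, against 5.0% and 90.9%.

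**The case against.** The strongest reply is that a t test after stratified allocation is valid. It is unbiased, it does not exceed its nominal error rate, and near 80% nominal power it does not fall below that power whatever the strata explain. Power is lost only against an analysis the plan never proposed. The fall to 67.7% requires a trial sized for an adjusted analysis, and nothing in the document suggests that. All of this is correct, which is why the table based on the t test's own nominal power is the fairer guide.

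The benefit also needs prognostic strata. With 32 patients and 8 strata, main effects gain only 0.7 points at R² = 5% (81.1 − 80.4) and lose 1.5 at R² = 0 (79.7 − 78.2). Fitting every stratum cell is worse than the t test at 0 and 5% and about level at 10%. This limits how the adjustment should be made but does not remove the case for it: with few strata the cost is close to nil, and the main-effects model gains in every simulated setting from 10% upwards.

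Two further points have some force. Baseline values are collected, and if the model also included them the strata might explain less of what remains than the range used here. And the plan is written in the past tense: if the outcomes had already been analysed, a change of test would be post hoc. Neither makes stratum adjustment wrong.

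**Conclusion.** The concern holds. The plan randomises by strata and then tests without them. If the strata are prognostic, the week 6 and week 12 t tests are conservative and forgo power that an adjusted analysis would keep. For R² between 10 and 30%, the actual type I error is about 3.9% down to 1.9% instead of 5%, and about 3 to 7.5 points of power are forgone when the t test's nominal power is 80%. If the strata explain nothing, nothing is lost.

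These sizes rest on assumed values of R², a two-sided test and, for the simulations, assumed patient numbers, strata and block size. The loss in this trial cannot be computed from the document. The plan should be changed, but the trial's validity is not in question.

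**What to change.** Name the stratification factor or factors used in the block randomisation. For the week 6 and week 12 between-group comparisons, replace the t test with a linear model (GLM in SPSS, the package already named) containing treatment and those factors. If there are many strata, enter the factors as main effects only and not as every stratum cell.

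The change is one of SAP wording. The data should already exist, since each patient's stratum must have been known in order to allocate by stratum; this is inferred, not stated. If the outcomes have already been analysed, report the stratum-adjusted model as a reanalysis and label it so.

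The statistical cost is a few degrees of freedom. In the least favourable simulated case (32 patients, 8 strata, none prognostic), main effects cost about 1.5 points of power and all stratum cells about 3.7 (79.7 − 76.0). With 60 patients the costs are 0.4 and 0.9 points. With 32 patients and 2 strata, neither prognostic, the cost is about 0.2 points (80.2 against 80.0).

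### The week-6 and week-12 group comparisons ignore both the baseline value and the randomisation strata, giving up precision if baseline predicts follow-up and running conservative if the strata are prognostic

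*Combined protocol and SAP*

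**What the plan says.** The Statistical Analysis Plan compares the groups as follows: "Differences between the two groups at baseline and at six and twelve weeks were tested by Independent-samples t test". It names no covariate, change score, mixed model or stratum term for this comparison. The only stated use of the link between baseline and follow-up is inside each arm: "Paired t tests were used for within-group analyses". The significance rule is "P values <0.05 were considered significant", with sidedness not stated.

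The Study Protocol shows that the unused information exists. On measurement it says "All data were collected at baseline, 6 and 12 weeks", and patients were allocated "in a ratio of 1:1 through the stratified block randomization method". The stratification factors and block size are not given.

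**The concern.** The paired tests use baseline but do not compare PrT with HA, so the treatment comparison rests on follow-up values alone. Two consequences follow, each under a condition.

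1. **If baseline predicts follow-up** (correlation ρ), the t test leaves explainable variation in its error term. A chance baseline difference of b SD also carries about ρ × b SD into the follow-up difference. The plan tests baseline differences but does not say what to do with the result.
2. **If the strata are prognostic**, stratified allocation removes their variation from the true error of the estimate. The t test still counts that variation in its reported standard error, so intervals are too wide and the type I error falls below 5%.

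At stake is power. A difference between two injection treatments could be missed, and a non-significant result read as no difference. The point concerns continuous outcomes only, not side effects or other categorical variables.

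**Working it through.** **Inputs.** From the documents: two groups, 1:1 allocation, stratified blocks, baseline collected, threshold 0.05. Assumed, because the documents are silent: two-sided testing; ρ of 0.3, 0.5 or 0.7; total N of 40 to 100; strata explaining 10%, 20% or 30% of outcome variance. The plan has no sample-size or power figure to reproduce.

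**Step 1: baseline adjustment, large sample.** The variance ratio of ANCOVA to the t test is 1 − ρ². The SE reduction is 1 − √(1 − ρ²). Where the t test has 80% power, ANCOVA has Φ((1.960 + 0.842)/√(1 − ρ²) − 1.960).

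| ρ | Variance ratio | SE reduction | Power |
|---|---|---|---|
| 0.3 | 0.91 | 4.6% | 83.6% |
| 0.5 | 0.75 | 13.4% | 89.9% |
| 0.7 | 0.51 | 28.6% | 97.5% |

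In sample-size terms, for an assumed 0.5 SD difference and 80% power, the t test needs 63 per arm. Baseline adjustment needs 58, 48 or 33.

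**Step 2: small-sample cost, baseline only.** The ratio becomes (1 − ρ²)(N − 3)/(N − 4).

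- N = 40: 0.935, 0.771, 0.524.
- N = 100: 0.919, 0.758, 0.515.
- At ρ = 0 the cost is 37/36 = 1.028 (N = 40) or 97/96 = 1.010 (N = 100).
- Setting the ratio to 1 gives a break-even ρ of 1/√(N − 3): 0.164 at N = 40 and 0.102 at N = 100.

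A simulation at N = 40 (40,000 trials, t test at 80% power) fitted ANCOVA with baseline and one stratum term. Power was 82.5%, 88.8% and 97.2% for the three correlations, and 78.7% at ρ = 0.

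**Step 3: chance imbalance.** One standard error of the baseline difference is 2/√N SD, which is 0.32 SD at N = 40 and 0.20 SD at N = 100. Multiplied by ρ, it shifts the unadjusted follow-up difference by 0.09, 0.16 or 0.22 SD at N = 40, and by 0.06, 0.10 or 0.14 SD at N = 100.

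**Step 4: prognostic strata.** Let R² be the share of outcome variance that the strata explain, with baseline independent of the strata. The reported SE is too large by 1/√(1 − R²) − 1. The large-sample type I error is 2(1 − Φ(1.960/√(1 − R²))). Where the strata-adjusted test has 80% power, the t test has Φ(2.802 − 1.960/√(1 − R²)).

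| R² | SE excess | Type I error, formula | Type I error, simulated (N 40 to 100) | t-test power |
|---|---|---|---|---|
| 10% | 5.4% | 3.9% | 3.8–4.0% | 76.9% |
| 20% | 11.8% | 2.8% | 2.8–3.0% | 72.9% |
| 30% | 19.5% | 1.9% | 1.9–2.1% | 67.7% |

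The simulations used two strata, either exactly balanced (60,000 trials) or in permuted blocks of 4 with incomplete last blocks (40,000 trials). A separate simulation with four strata at N = 60 and 120 gave 2.8–3.2% for the t test at R² = 20%. The model with baseline and strata stayed at 4.5–5.2% in every setting. With non-prognostic strata the t test was at 4.8–5.3%, which confirms that the effect is conditional.

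**The case against.** The strongest reply is that this is a preference about efficiency and not an error. The t test does not inflate false positives, no actual imbalance is shown, and both harms depend on conditions that the documents do not settle. That is correct, and it limits the point to a recommended improvement.

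A second reply is that the full model can cost something in a small trial with many strata. This also stands. With 8 non-prognostic strata at N = 40 and blocks of 4, simulated power (t test against adjusted) was 79.8% against 76.0% at ρ = 0, 80.0% against 77.5% at ρ = 0.164, and 80.3% against 80.4% at ρ = 0.3. The break-even values in Step 2 therefore apply to adjustment for baseline alone; the full model in this setting breaks even near ρ = 0.3. At ρ of 0.5 or more, adjustment gained in every setting tried.

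Third, the two effects cannot be added if a stratum tracks baseline severity. In that case large baseline imbalances would be rarer, and conservatism would be the main consequence.

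Finally, the strata part of the remedy cannot be carried out until the factors are named. That makes naming them part of the fix. It does not remove the problem.

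**Conclusion.** The concern holds. The planned week-6 and week-12 comparisons use neither the baseline value nor the strata, and nothing elsewhere in the document supplies an adjustment. The test is valid (type I error at or below 5%) and unbiased over repeated randomisations, and any baseline imbalance would be chance, not systematic bias.

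The omission is certain; the size of the loss in this trial is unknown. Under the assumed ranges, adjusting for baseline adds about 4 to 18 points to 80% power in large samples. At N = 40, with baseline and one stratum term, it adds about 3 to 17 points. Prognostic strata would leave the t test about 3 to 12 points below an 80% adjusted test. On the other side, the cost when baseline predicts nothing is about one point at N = 40 with one stratum term, and about four points with 8 non-prognostic strata. The plan should be changed, but its results would not be invalid without the change.

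**What to change.** For each continuous outcome, replace the week-6 and week-12 t tests with ANCOVA (general linear model in SPSS). Model the outcome at that visit on treatment group, with that outcome's baseline value and the randomisation stratification factors as covariates. Name those factors in the Statistical Analysis Plan. Report the adjusted mean difference between groups with its 95% CI.

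If analysis has not started, the cost is a change of wording and the naming of the factors. If it is finished, as the past tense in "was used to conduct the analysis" may mean, fit the same model as a labelled additional analysis beside the planned t test, so that the planned result is not replaced after the fact. Either way no new data or software are needed: one model per continuous outcome and visit. The price in residual degrees of freedom is one for baseline plus those for the strata, which is small unless the strata are many relative to the sample size.

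### By default the week-12 t test uses only patients measured at week 12 and ignores the week-6 response of those who leave, so uneven response-related withdrawal would bias it

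*Combined protocol and SAP*

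**What the plan says.** The Study Protocol section describes patients "randomly assigned into two groups (PrT group, HA group) in a ratio of 1:1 through the stratified block randomization method" and gives the visit schedule: "All data were collected at baseline, 6 and 12 weeks".

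The Statistical Analysis Plan section gives the between-group method in one sentence: "Differences between the two groups at baseline and at six and twelve weeks were tested by Independent-samples t test". Within each arm, "Paired t tests were used for within-group analyses". The decision rule is "P values <0.05 were considered significant".

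Neither section states an analysis set, a rule for missing values, an expected dropout rate, a sample size, a joint analysis of the visits or a sensitivity analysis.

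**The concern.** An independent-samples t test at week 12 can use only patients who have a week-12 value. Someone who attends week 6 and then leaves is absent from that test unless a step is added, and the plan names none. The week-6 measurement is likely to be one of the best available predictors of the missing value, yet nothing carries it into the week-12 comparison.

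Two things follow. The week-6 and week-12 results may describe different sets of patients. And the week-12 comparison is protected by randomisation only if leaving is unrelated to response, or is related to it in the same way and to the same extent in both arms. If patients with a poor week-6 response leave more often from one arm, that arm's week-12 mean is taken over its better responders and the arm looks better than it is.

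This is a different matter from adjusting for baseline. A baseline-adjusted comparison of patients with week-12 data would leave out the same patients and ignore the same week-6 values.

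**Working it through.** The plan has no sample size, power or dropout figure to reproduce, so the check is of what the stated method does under stated assumptions.

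**Inputs from the document:** two arms at 1:1; visits at baseline, week 6 and week 12; a separate t test at each visit; significance at 0.05 (sidedness not stated; two-sided assumed).

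**Assumptions (none is in the document):** outcome with SD 1 at each visit, higher meaning worse; no true difference; week-6 to week-12 correlation ρ of 0.5 or 0.7; withdrawal after week 6 following a logistic model on the week-6 value, with slope 0.5, 1.0 or 1.5 log-odds per SD (odds ratios of about 1.6, 2.7 and 4.5) and the intercept set to give the withdrawal rate; 30 or 60 patients per arm for error rates.

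**Step 1. Mean week-6 value of those who stay.** Call it m = E[Y6 | stays]. By numerical integration over a standard normal Y6:

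| Slope | 5% leave | 10% | 15% | 20% | 25% |
|---|---|---|---|---|---|
| 0.5 | −0.0247 | −0.0488 | −0.0726 | −0.0962 | −0.1195 |
| 1.0 | −0.0471 | −0.0908 | −0.1326 | −0.1732 | −0.2132 |
| 1.5 | −0.0648 | −0.1217 | −0.1751 | −0.2266 | −0.2769 |

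**Step 2. Bias of the week-12 t test.** Since E[Y12 | Y6] = ρ·Y6, the stayers' week-12 mean is ρ·m, and the bias is ρ·(m_A − m_B). Example: slope 1.5, 5% v 20%, ρ = 0.7 gives 0.7 × (−0.0648 + 0.2266) = 0.113 SD. All results in SD, for ρ = 0.5 / 0.7:

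| Slope | 5% v 15% | 5% v 20% | 10% v 25% |
|---|---|---|---|
| 0.5 | 0.024 / 0.034 | 0.036 / 0.050 | 0.035 / 0.049 |
| 1.0 | 0.043 / 0.060 | 0.063 / 0.088 | 0.061 / 0.086 |
| 1.5 | 0.055 / 0.077 | 0.081 / 0.113 | 0.078 / 0.109 |

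With the same rate and the same slope in both arms, m_A = m_B and the bias is zero. If patients doing well leave instead, the slope changes sign, m changes sign and the bias reverses. Equal rates alone are not enough: with 20% leaving each arm at slope 1.5, but worse patients from one arm and better patients from the other, the size is ρ × 2 × 0.2266 = 0.23 to 0.32 SD.

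**Step 3. Effect on the 0.05 rule.** The stayers' week-12 variance is 1 − ρ² + ρ²v, where v is their week-6 variance. For slope 1.5, 5% v 20%, ρ = 0.7 and 60 per arm, v is 0.9267 and 0.8159, so the variances are 0.964 and 0.910, on 57 and 48 patients. SE = √(0.964/57 + 0.910/48) = 0.189, and 0.113/0.189 = 0.60. The chance of p < 0.05 is P(Z > 1.36) + P(Z < −2.56), about 0.09. Across 30 to 60 per arm and both correlations, the 5% v 20% case gives about 0.06 to 0.09 at slope 1.5 and 0.052 to 0.058 at slope 0.5. Simulation at slope 1.5 (2,000 trials per setting) gave 0.06 to 0.08, and about 0.05 with no withdrawal or purely random withdrawal.

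**Step 4. Using the week-6 value.** Regress week 12 on week 6 among stayers and average over everyone in the arm. The expected result is ρ·m + ρ·(0 − m) = 0, so the bias vanishes. In the simulations it was within 0.02 SD of zero, consistent with sampling error.

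**The case against.** Four stronger readings are tempting, and the document supports none of them.

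- **That the plan has a rule excluding patients who leave.** It has no such rule. Exclusion is what the named test does by default, and an unstated imputation cannot be ruled out. What is documented is a test chosen without an analysis set or a missing-data method.
- **That the week-6 data are thrown away.** Week 6 has its own between-group test, and its values can enter the paired tests. They go unused only in the week-12 comparison.
- **That a patient who seeks other treatment is removed.** Anyone measured at week 12 enters the week-12 test. Nothing in the document removes a patient for other treatment, and the model proposed here does not address that separate question.
- **That the result is biased, in favour of the arm with more withdrawal.** This needs uneven, response-related withdrawal, with poor responders leaving. If recovered patients stop attending, the sign reverses.

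On the other side, the sentence "All data were collected at baseline, 6 and 12 weeks" might be read as showing complete follow-up. It more naturally gives the schedule, and settles nothing about who withdrew. Blinding helps somewhat, since "The patients and the researcher who were responsible for the analyzing of the data were blinded to the randomization results", but a patient can leave over a poor response without knowing the assignment.

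The objection on size stands. The slope drives the result and 1.5 is steep. At 0.5 the bias is at most 0.05 SD and the error rate barely moves. The zero bias in Step 4 is also built in, because withdrawal was made to depend on the observed week-6 value alone. It says nothing about withdrawal that depends on later, unseen values, and an observed-case t test would not probe that either.

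**Conclusion.** The point holds as a conditional weakness that is cheap to remove. Followed as written, the week-12 comparison rests on patients measured then and makes no use of the week-6 response of those who left. Over the assumed withdrawal patterns (5% v 15% to 10% v 25%, worse patients leaving, correlation 0.5 to 0.7, no true difference), the bias is about 0.02 to 0.05 SD at slope 0.5, 0.04 to 0.09 SD at 1.0 and 0.05 to 0.11 SD at 1.5. These are modest amounts. They illustrate what could happen and do not estimate what did, because the document gives no dropout rate, sample size or correlation. The change is worth making, but the material does not show that the trial's conclusion is unsound.

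**What to change.** For each continuous outcome, replace the separate week-6 and week-12 t tests with one linear mixed model for repeated measures, which SPSS 23 can fit:

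- Include all randomised patients with any recorded outcome value, in their assigned group.
- Take baseline, week 6 and week 12 as the repeated outcomes, with group, visit, group-by-visit and the randomisation stratification factors (which the document does not name and should), and an unstructured covariance.
- Read the week-12 and week-6 group differences from this model.

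Report withdrawals and their reasons by arm. Keep the observed-case t test as a supporting analysis. Add a simple missing-not-at-random sensitivity analysis in which the unseen week-12 values are shifted by a range of amounts (delta), separately by arm, to see how large a shift would change the conclusion.

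The cost is SAP wording and slightly more analysis, with no extra patients, visits or measurements. If nobody withdraws, the model's group differences should agree closely with the planned t tests. The remaining weakness is that the model assumes withdrawal depends only on observed values. That is less demanding than what the t test needs but cannot be tested, which is why the delta analysis belongs with it.

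### Change within each arm is significance-tested in a design with no untreated or placebo arm, and the plan does not say that such change cannot be read as an effect of the injection

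*Combined protocol and SAP*

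**What the plan says.** The Study Protocol section describes a "single-blind randomized clinical trial with parallel group and allocation ratio was 1:1", with patients "randomly assigned into two groups (PrT group, HA group) in a ratio of 1:1". No third arm is described. The abbreviations PrT and HA are not expanded. That both arms are injected is read from the title, which refers to injection therapy, and from the statement that "patients were monitored if they had any side effects from the injection", which makes no distinction between arms. On timing: "All data were collected at baseline, 6 and 12 weeks".

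The Statistical Analysis Plan section gives two sets of tests for continuous outcomes. Between arms: "Differences between the two groups at baseline and at six and twelve weeks were tested by Independent-samples t test". Within arms, followed by the one criterion that closes the section and covers everything before it: "Paired t tests were used for within-group analyses. P values <0.05 were considered significant". It does not say which pairs of visits the within-arm tests compare. The plan does not label the within-arm tests descriptive, name a primary comparison, or say how a significant within-arm change is to be interpreted.

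**The concern.** The null hypothesis of a paired t test is that mean change over time is zero. It is not that the injection has no effect. Over 12 weeks, change from baseline can combine an effect of the injected agent with the natural course of the condition, regression to the mean (if patients enter while their symptoms are bad) and the response to being injected at all. With no untreated or placebo arm, nothing in the design separates these parts. Randomisation protects the PrT versus HA contrast, and the paired tests do not use that contrast.

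Because the same significance rule applies to both kinds of test, two misreadings stay open:

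- Both paired tests are significant, and the report says that both injections are effective.
- Only one paired test is significant, and the report says that this injection works and the other does not, although the arms may not differ.

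A baseline-adjusted between-group analysis, or a multiplicity correction across visits, would close neither. Both improve the between-group test and leave the paired tests as they are.

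**Working it through.** **The plan's own figure.** There is none to reproduce. The documents give no sample size, standard deviation, effect size or expected recovery. What follows is an illustration over assumed values.

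**Inputs from the documents.** Two arms, 1:1; a paired t test in each arm; significance at 0.05. Sidedness is not stated; two-sided is assumed.

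**Assumed inputs.** Neither injection has any effect. Both arms improve equally for other reasons, by d standard deviations of the change score. One outcome is tested at one visit. The number per arm, n, is 20, 30 or 50.

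**Step 1: one arm.** The paired t statistic follows a noncentral t distribution with n − 1 degrees of freedom and noncentrality d × √n. Let p be the probability that it exceeds the upper 2.5% point of the central t, that is, a significant improvement. For n = 30 and d = 0.5, the critical value is 2.045 and the noncentrality is 0.5 × √30 = 2.74, which gives p = 0.754.

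**Step 2: two arms.** The arms are independent, so both are significant with probability p² and exactly one with probability 2p(1 − p). For n = 30 and d = 0.5: 0.754² = 0.57, and 2 × 0.754 × 0.246 = 0.37.

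| n per arm | d | p (one arm) | both arms | exactly one |
|---|---|---|---|---|
| 30 | 0.1 | 0.076 | 1% | 14% |
| 30 | 0.3 | 0.355 | 13% | 46% |
| 30 | 0.5 | 0.754 | 57% | 37% |
| 30 | 0.8 | 0.988 | 98% | 2% |
| 20 | 0.5 | 0.565 | 32% | 49% |
| 50 | 0.5 | 0.934 | 87% | 12% |

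**Step 3: the between-group test under the same conditions.** A shift common to both arms cancels in the difference between them. In a simulation of 40,000 trials per setting (baseline to follow-up correlation 0.5; n = 20, 30 and 50; d = 0.5 and 0.8), the independent-samples t test at one visit rejected in 4.9% to 5.1% of trials. It keeps its nominal level.

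**Step 4: what the percentages are.** In these scenarios patients do improve, so rejecting no change over time is correct. The table gives power to detect real change. Its entries become rates of false conclusions only if a significant change is attributed to the injection.

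**The case against.** The strongest reply is that the plan does not make the error. It nowhere says that a significant paired test shows efficacy, or that the arms will be compared by which of the two P values falls below 0.05. It does plan a direct randomised comparison at both follow-up visits, lists it before the paired tests, and that comparison is sound under shared recovery. To conclude that one injection works and the other does not, a reader would have to ignore a between-group result that the plan also produces. All of this stands.

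Three stronger readings are therefore not supported. A reader might infer that the plan commits the investigators to within-group efficacy claims; the text neither states nor excludes them. A reader might take the table as inflated type I error and set it against 5%. The tests are not wrong about change, and a two-arm probability should not be compared with a per-test rate in any case: with no change at all, the chance that at least one arm is significant is 1 − 0.95² = 9.75%. A reader might also infer that the PrT versus HA comparison is compromised; it is not, on this point.

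Two further objections hold in part. The values of d have no anchor in the documents, and at d = 0.1 with 30 per arm both tests are significant in only about 1% of trials. Also, a 95% confidence interval for mean change that excludes zero is the same test as a paired P below 0.05, so replacing one with the other changes no inference by itself. The interpretive sentence in the fix does the work.

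What the reply does not remove is the silence of the plan. If the between-group test is not significant, two significant paired tests remain available under the same rule, with nothing to say what they cannot show.

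**Conclusion.** The point holds as a gap in wording and interpretation, confined to the paired tests. The plan puts uncontrolled change over time on the same inferential footing as the randomised comparison and states no limit on how it may be read. The analysis of PrT versus HA is not invalidated.

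How much this matters depends on how far patients improve for reasons other than the injected agent, which the documents do not indicate. With 30 per arm and shared improvement of 0.3 to 0.8 SD of change, a pattern open to one or other misreading (both arms or exactly one) arises in roughly 58% of trials or more: 13% + 46% before rounding at d = 0.3, and over 90% at d = 0.5 and 0.8. At d = 0.1 it is about 15%. These figures assume no injection effect, equal improvement in both arms, one outcome and one visit. They count as false conclusions only if the change is attributed to the injection. That both arms are injected is a reasonable inference from the title and the side-effect statement, not an explicit one.

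This is a cheap improvement that should be made.

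**What to change.** In the Statistical Analysis Plan, replace the sentence "Paired t tests were used for within-group analyses" with:

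> Within-group change from baseline to weeks 6 and 12 is presented descriptively (mean change with 95% CI), without significance tests, and is not interpreted as an effect of that injection because there is no untreated or placebo arm. Conclusions about treatment rest on the randomised PrT minus HA difference with its 95% CI.

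For conclusions about treatment, apply the 0.05 criterion to the between-group tests only.

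The cost is wording: no extra patients, visits or data. The within-group P values are given up, together with any claim that each injection is effective on its own, which this design cannot support.
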